We will define the pharmacokinetics of buprenorphine and determine if there is a better way to gauge dosing based on objective, physiological parameters of satiety. We will also determine which maternal, placental or fetal factors impact the risk of Neonatal Abstinence Syndrome (NAS) and will define neonatal exposure to buprenorphine through breast milk.

Our specific aims are:

1. To determine the impact of pregnancy on the pharmacokinetics of buprenorphine (BUP) and its metabolites after sublingual administration.
2. To determine the impact of patient covariates such as age, race, co-medications and single nucleotide polymorphisms of BUP metabolizing enzymes (CYP3A4/5; UGT) and transporters (P-glycoprotein) on the variability in exposure of BUP and its metabolites in pregnant women.
3. To evaluate potential pharmacodynamic endpoints for dosing sublingual BUP during pregnancy and the non-pregnant state.
4. To evaluate the relationship between maternal and umbilical cord BUP and its metabolite concentrations.
5. To evaluate the relationship between maternal, placental and neonatal covariates such as concentrations of BUP and its metabolites in maternal and umbilical cord blood and maternal and newborn hair to NAS severity and duration.
6. To evaluate potential infant exposure to BUP and metabolites through breast milk.

We anticipate that the currently recommended dose of buprenorphine will be insufficient in many women to satisfy their drug cravings. Although some part of this craving may be psychological rather than physiologic, we anticipate that alterations in physiology due to pregnancy may result in more rapid metabolism and elimination of this medication and thus provide a level of medication that is sub-therapeutic. We also anticipate that the poor relationship between NAS and maternal dosage of buprenorphine may in part be explained by maternal or placental factors which impact fetal exposure.

D. Approach - Overall Strategy Methodology and Analysis

D.1. Study Overview

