We will enroll eligible, consenting pregnant women who are receiving sublingual BUP (subutex) in a supervised hospital or outpatient clinical setting because of their opiate addiction. Due to the possibility of limited subject availability at individual centers, recruitment can target subjects receiving pregnancy care at other institutions. Likewise, since buprenorphine is commonly not dispensed in a hospital setting, subjects may need to be recruited from clinics where buprenorphine is provided to pregnant women as part of a structured maintenance program. To facilitate enrollment, recruitment can target one or more specific aims as summarized below.

For Specific Aims 1 and 3:

We will recruit 40 eligible, consenting pregnant women to an 'extensive sampling' pharmacokinetic (PK) study in which they will be studied three times: once between 8 0/7-20 6/7, once between 21 0/7-35 6/7 and once at 4-6 weeks post-delivery. Studies done during pregnancy should be at least 12 weeks apart. We will also obtain patient demographics and medical history.

We will encourage subjects to complete as many PK studies as possible; however, subjects are only required to complete one PK study in order to participate in this portion of the study. Each study is 13 hours in length for BID dosing, 9 hours for TID dosing, 7 hours for QID dosing, and 6 hours for five times daily dosing.

Each PK study will be performed after the subject has been on a stable dose of BUP for a minimum of 7 days. Physiologic testing (pupillometry, galvanic skin response, and heart rate), COW and craving scores will be performed before the daily dose of BUP is taken.

Measurement Type	Dosing	Length of Study	No. of Measurements
Blood (BUP/metabolite)	BID	13 hrs	Baseline + 12 additional
Physiologic			Baseline + 9 additional
Blood (BUP/metabolite)	TID	9 hrs	Baseline + 12 additional
Physiologic			Baseline + 9 additional
Blood (BUP/metabolite)	QID	7 hrs	Baseline + 10 additional
Physiologic			Baseline + 7 additional
Blood (BUP/metabolite)	5 times/daily	6 hrs	Baseline + 10 additional
Physiologic			Baseline + 7 additional

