Maternal cotinine and catecholamines will also be measured in the blood and related to the physiologic variables and to maternal craving scores. A maternal hair sample will be obtained around the time of delivery when possible for determination of buprenorphine and metabolite content. Pharmacokinetic modeling will be performed for both the parent compound and its major metabolites. We will determine the impact of the CYP and UGT SNPs on plasma and umbilical cord blood concentrations of BUP and its metabolites.

We will also seek to enroll subjects in an elective ancillary study to determine how rapidly the metabolizing enzyme activity changes after delivery. For those agreeing, we will collect 1-2 maternal blood samples at least 2 days apart while the patient is in the hospital. We will continue to collect weekly maternal blood samples during the subject's routine visits to the MWH BUP clinic for 4 weeks.

For Specific Aims 2, 4 and 5:

Blood will be obtained and genotyping of enzymes responsible for the metabolism of BUP (CYP3A and UGT) will be performed. Given that norbuprenorphine is a substrate for P-glycoprotein (P-gp), genotyping for Pgp will also be performed. We will also evaluate peripheral blood mononuclear cells (PBMCs) as a surrogate marker of metabolic enzymes and transporters. The expression of drug metabolizing enzymes and transporters in the PBMCs will be correlated with the plasma concentrations of BUP and its major metabolites.

Those women who do not participate in the PK study described in the section above (for specific aims 1 and 3) will be consented to participate in some or all of the other components of the study. In those women, we will obtain a blood specimen at the time of consent and record the time of blood draw, the time of the last dose administration, and the dosing history. Subjects recruited to the other components of the study will not reduce the sample size requirements (n=40) for the parent trial but will be used to more precisely model BUP pharmacokinetics.

The following applies to all enrolled women whether or not they are participating in the PK study.

- A maternal blood sample will be obtained from the mother prior to delivery. A portion of the placenta, umbilical cord, and umbilical cord blood will be collected at delivery and immediately frozen.

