Patients will be at steady state when the pharmacokinetic studies are performed. This will be documented by comparing the concentration at time 0 and at 12 hrs. (less than 20% variation). Plasma concentration-time profiles will be analyzed using both non-compartmental and population pharmacokinetic modeling and simulation approaches. Data will be analyzed using WINNONLIN and NONMEM software. We will compare various pharmacokinetic parameters between pregnant and non-pregnant (postpartum) subjects using a paired t-test as described previously. This will include all non-compartmental data (C_{max}, T_{max}, AUC(0-t), AUC(0-∞), k_e, λ_Z, CL/F, CLR, V_d/F, V_{ss}, AUMC, and MRT). Population pharmacokinetic model will be developed using nonlinear mixed effects modeling software (NONMEM version 7.1; ICON Development Solutions, [name]), GNU Fortran 95 compiler and PLT tools (version 5.1.0). The general linear model under steady state will be constructed using ADVAN5 SS5 subroutines. In order to identify the covariates that influence the pharmacokinetics of BUP, the following covariates will be evaluated: maternal age (years), body weight (kg), race, gestational age, serum albumin, serum creatinine (mg/dL), salivary PH, buprenorphine dose, tablet size and co-medications and SNPs of the various metabolizing enzymes. For covariate selection, univariate analysis with stepwise forward addition ($p < 0.01$) and backward elimination ($p < 0.001$) procedures will be followed. The covariates that significantly influence the pharmacokinetics of BUP and its metabolite will be incorporated in the final model. The predictive performance of the model will be internally evaluated using prediction corrected-visual predictive check, where 1500 data sets will be simulated using the parameter estimates in the final model. The 50th percentile concentration (median) and the 5th and 95th percentile concentrations (90% prediction interval) will be plotted and compared to the observed concentrations. The data obtained will be used to validate the predictions of SIMCYP-PBPK simulation from the basic/translation project.

D.6. Preliminary Data Relevant to the Primary Outcome

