We have developed a HPLC-MS-MS assay for BUP and metabolites with a lower limit of quantitation of the assay for BUP (BUP), of 0.05 ng/ml, while that for nor-BUP is 0.5 ng/ml. We have performed an intensive PK study on 12 subjects. The dose-adjusted AUC in the third trimester of pregnancy (2.4 ng/ml).hr was lower than in the postpartum period (4.0 ng/ml).hr while clearance is higher in pregnancy (589 L/hr) than in the postpartum period (288 L/hr). There was a large variation (cv = 50%) in both AUC and clearance values. None of the subjects in this cohort was studied in the first half of pregnancy.

D.7. Potential Problems, Alternative Strategies, Benchmarks

Recruitment is a potential problem in any clinical trial and if other sites in the OPPTB do not have access to patients on BUP in their own institutions they may have difficulty recruiting subjects. These patients have difficulty with compliance to drug treatment regimens so dropout may be higher than in most clinical trials. Postpartum studies are difficult because of childcare issues and this may hamper recruitment. These challenges can be overcome by identifying physicians and clinics that write prescriptions for BUP and care for such patients. The childcare issue can be addressed by financial incentives or by allowing the mother to bring her baby to the CRC during study days.

D.8. Feasibility

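### Aim 2 asks how large covariate and SNP effects are, but the only specified method is stepwise selection at p < 0.001, with no estimate planned for covariates that are not retained

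*Combined protocol and SAP*

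**What the plan says.** Section C gives Aim 2 as: "To determine the impact of patient covariates such as age, race, co-medications and single nucleotide polymorphisms of BUP metabolizing enzymes", continuing to transporters, on variability in exposure. D.5.xii lists the impact of metabolizing-enzyme polymorphisms on plasma concentration as a secondary maternal outcome. D.5.xiii (Data Analysis Plan) assigns covariates such as maternal genotype to population PK analysis.

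The method is in D.5.xiii (Secondary Hypotheses). The candidates are maternal age, weight, race, gestational age, albumin, creatinine, "salivary PH, buprenorphine dose, tablet size and co-medications and SNPs of the various metabolizing enzymes". That is ten named covariates plus an unstated number of SNPs. Then "univariate analysis with stepwise forward addition ($p < 0.01$) and backward elimination ($p < 0.001$) procedures will be followed", and "The covariates that significantly influence the pharmacokinetics of BUP and its metabolite will be incorporated in the final model". The internal evaluation is a prediction-corrected visual predictive check.

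On the sample, D.1 says: "We will recruit 40 eligible, consenting pregnant women to an 'extensive sampling' pharmacokinetic (PK) study", with up to three visits each, although "subjects are only required to complete one PK study in order to participate in this portion of the study". Women outside the PK study give a timed sample at consent. They do not reduce the requirement of 40 "for the parent trial but will be used to more precisely model BUP pharmacokinetics". Their number is not stated. On variability, D.6 reports: "There was a large variation (cv = 50%) in both AUC and clearance values".

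The documents give no power for Aim 2, no prespecified full covariate model, no shrinkage or bootstrap correction, and no interval for a covariate that is not retained.

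**The concern.** A selection rule tells the reader which covariates passed. It does not tell how large each effect is or how precisely it is known, and that is what Aim 2 asks. With a strict limit and a small sample there are two consequences. Moderate effects mostly drop out of the final model and leave no estimate behind. Those that stay in are the ones whose estimates came out large by chance, so the final-model values overstate them.

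This matters because section B expects to show that dosing can be adjusted using patient covariates, and inflated or missing effects would feed into that use. The point concerns between-woman covariates (SNPs, age, race, co-medications), not the pregnancy/postpartum term.

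**Working it through.** **The plan's own figure.** D.5.xiii gives 37 women for a 50% difference in dose-adjusted AUC (2.34 ± 1.82). With a difference of 0.5 × 2.34 = 1.17, two-sided alpha 0.05, and the stated 0.80 read as power, n = 2 × 1.82² × (1.960 + 0.842)² / 1.17² = 38.0, within one of the stated 37. This supports the primary comparison and says nothing about Aim 2.

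**Inputs from the documents.** 40 women (D.1); backward limit p < 0.001 (D.5.xiii), which is binding; CV 50% (D.6). D.5.xiii also implies CV 1.82/2.34 = 78% in late pregnancy and 2.8/4.0 = 70% postpartum.

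**Assumptions not in the documents.** One well-estimated log CL/F per woman; lognormal variation, with the CV taken as between-woman; a two-group SNP effect; 20-50% carriers; a two-sided 1-df test, z = 3.29; true effect 1.5-fold or a halving.

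**Formulas.**
- Log-scale SD: ω = √ln(1 + CV²) = 0.472, 0.631 and 0.689 for CV 50%, 70% and 78%.
- SE of the log ratio = ω × √(1/n₁ + 1/n₂). For 8 carriers against 32 at CV 50%: 0.472 × √(1/8 + 1/32) = 0.187.
- Smallest estimate that can be retained = exp(3.29 × SE).
- Probability of retention = 1 − Φ(a), with a = 3.29 − d/SE, where d = ln 1.5 = 0.405 or ln 2 = 0.693.
- Mean retained estimate (log mean, back-transformed) = exp(d + SE × φ(a)/(1 − Φ(a))).

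**Results for 40 women.** Ranges run from CV 70% to CV 78%.

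| CV | Carriers | SE | Smallest retainable | 1.5-fold retained | Mean when retained | Halving retained |
|---|---|---|---|---|---|---|
| 50% | 50% | 0.149 | 1.63 | 28% | 1.79 | 91% |
| 50% | 30% | 0.163 | 1.71 | 21% | 1.88 | 83% |
| 50% | 20% | 0.187 | 1.85 | 13% | 2.03 | 66% |
| 70-78% | 50% | 0.200-0.218 | 1.93-2.05 | 10-8% | 2.12-2.26 | 57-46% |
| 70-78% | 20% | 0.250-0.272 | 2.27-2.45 | 5-4% | 2.52-2.73 | 30-23% |

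In every row the smallest retainable estimate exceeds 1.5, so an estimate equal to the true 1.5 cannot be retained.

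**Check by simulation.** The two-step rule was run 1,500 times with 12 candidates, using a linear model on log clearance in place of NONMEM, at CV 50%. For carrier shares of 50/30/20%, a 1.5-fold effect was retained in 26/21/13% of runs with means 1.79/1.85/2.00, and 98-100% of retained estimates lay above the truth. A halving was retained in 88/79/60% with means 0.48/0.47/0.45, and 59-80% of those estimates were overstated.

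**More data, 1.5-fold effect, CV 50%, carriers 50/30/20%.**
- Three visits averaged per woman multiply the variance by (1 + 2ρ)/3. Retention is 51/40/26% at intraclass correlation ρ = 0.5 and 32/24/15% at ρ = 0.9.
- 40 extra women each carrying a quarter of the information give an effective N of 40 + 40/4 = 50. Retention is 40/31/19%.
- 80 fully informative women: 71/59/41%, with mean retained estimates 1.58/1.62/1.70.

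**The case against.** The strongest reply is that 40 is not the Aim 2 sample. D.1 recruits the 40 for Aims 1 and 3. For Aim 2 it adds women outside the PK study, and each PK woman may have three visits. This stands: retention at N = 40 with one visit is a reference case, and the answer depends on a number that the plan does not give. In the cases above retention stays near or below one half unless the extra data are substantial.

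Second, a strict limit restrains false positives when ten covariates and an open list of SNPs are screened, and D.5.xiii says that the aim there is to identify influential covariates. That is a fair defence of the rule for model building. It does not supply effect sizes for Aim 2.

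Third, D.3 concedes that the sample may be too small for some secondary questions, and maternal covariates are on that list. The concession favours showing intervals.

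A reader might infer several stronger things that the documents do not support:
- That non-retained SNPs will be reported as having no effect. The plan is silent on how they are reported.
- That any real 50% effect is usually missed. A halving at CV 50% is usually kept.
- That every retained effect is overstated. This is nearly so for a 1.5-fold effect at N = 40, but not in general.
- That nothing else bears on Aim 2. D.1 correlates PBMC enzyme and transporter expression with concentrations and says that SNP impact will be determined, without a method. D.5.xiii adds regressions with CYP3A4/5 expression. Stepwise selection is still the only method specified for the SNP, age, race and co-medication effects.

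**Conclusion.** The point holds for moderate effects at about the planned intensive sample. Under the stated assumptions a true 1.5-fold effect would usually drop out, and if kept would be reported too large. The shortfall is worse at the CVs that the sample-size section itself implies, and milder with repeat visits or many informative extra women. For large effects at CV 50% the plan performs acceptably.

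The result rests on assumed carrier shares, a two-group SNP effect and a simplified model. No calculation was made for age, race or co-medications, though the same selection rule applies to them. This is a minor to moderate matter for a secondary aim, and worth changing because the remedy is cheap.

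**What to change.** Keep the stepwise model for prediction. For Aim 2, add to D.5.xiii:

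- A table of the estimated effect on CL/F with a 95% confidence interval for every candidate covariate and SNP, retained or not. Take these either one at a time, each adjusted for pregnancy/postpartum period, or from one full model limited to a short list fixed before analysis. A full model with every SNP is debatable at this sample size.
- A statement that estimates from the selected model are not the Aim 2 effect sizes, and that non-retention is not evidence of no effect.
- The SNPs to be examined, and the expected number of women and samples in the population PK analysis.

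The cost is a few more model runs and one table, with no new patients, samples or visits. Intervals will be wide. At N = 40 the factor either way, exp(1.96 × SE), runs from 1.34 (CV 50%, 50% carriers) to about 1.7 (CV 78%, 20% carriers) for one covariate at a time. It is wider in a multi-covariate model: about 1.4-1.6 with 12 covariates at CV 50%. A true 1.5-fold effect at CV 50%, one covariate at a time, would carry an expected interval of about 1.12-2.01 (50% carriers) or 1.04-2.16 (20%). With many SNPs the intervals are descriptive and not adjusted for multiplicity, and the table should say so.
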